	We expect that 10% of the 2752 (elderly) patients will have influenza A or B. Of the 275, one third (~91) will be allocated to Groups 1, 2, and 3. Identical sample sets will be taken from each individual, so the diagnostic accuracy of the tests will be assessed in all 275 subjects.
	We expect that 5% of the 2752 (elderly) patients will have RSV A or B. Of the 137, one third (~45) will be allocated to the rapid molecular group (Group 2); the remainder (~90) will be allocated to the groups tested by traditional methods (Group 1 & 3). Identical sample sets will be taken from each individual, so the diagnostic accuracy of the tests will be assessed in all 137 subjects.
	While the numbers of patients with influenza and RSV who are allocated to the 'rapid' near patient or molecular tests are comparatively small, the impact of a 'viral' infection (RSV or influenza) infection on patient isolation, antimicrobial prescribing, and clinical outcomes may be compared using larger combined groups – i.e., Rapid influenza & RSV (i.e., Quickview + molecular tests) $n = (91 + 91 + 45) = 227$ Traditional influenza & RSV $n = (91 + 45 + 45) = 182$ .
Statistical power:	This has been estimated for one laboratory and two clinical endpoints for the elderly population only.
	Diagnostic accuracy Assuming that the average sensitivity/specificity of the tests is $80\%[90\%]$ then allowing for a 20% dropout rate, a sample of 2752 (2000) i.e. only 2 winters) elderly ( $\geq$ 65 years) patients randomised into the trial would enable the sensitivity/specificity to be estimated to within, i.e. 2SE, 7.6% (8.9%) [5.7% (6.7%)] for a disease prevalence of 10%, and 5.4% (6.3%) [4.0% (4.7%)] for a disease prevalence of 5%.
	Length of Stay 2752 patients would enable a Minimum Clinically Significant Difference (MCSD) [between diagnostic policies] of 1 day in the mean length of stay (assuming SD=6 days) to be detected at the 5% significance level with over 80% power, assuming a 20% dropout rate and adjusting for the fact that there are 3 groups.
	Appropriate Isolation Levels: 2752 patients would also enable a Minimum Clinically Significant Difference (MCSD) [between diagnostic policies] of an improvement in appropriate use of isolation facilities from 5% to 15% to be detected at the 1% significance level with over 95% power, assuming a 20% dropout rate and adjusting for the fact that there are 3 groups.

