#### 2.2 Observational objectives and hypotheses

In the Medical Admissions Units/Wards of the University Hospitals of Leicester, to:

11. Estimate the admission rates for influenza, RSV, and S pneumoniae in the target population.

The admission rates in the target population are higher for S pneumoniae than influenza A and B. The admission rates for influenza A and B are similar to those for RSV A and B.

12. Compare the clinical characteristics and economic burden of influenza A and B and RSV A and B.

The clinical characteristics and economic burden of influenza A and B and RSV A and B are similar.

13. Review the implications of rapid diagnosis on isolation policy, and review alternate approaches to managing the infection control issues.

Rapid near patient and/or molecular diagnostic tests will reveal more cases of influenza and RSV who require isolation than can be isolated. Alternate approaches to managing the infection control issues, such as the use of influenza neuraminidase inhibitors, may be pertinent.

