- Based on the above, we expect to recruit 747 participants with pneumonia, of whom at least one third (n=249) should have *S. pneumoniae* infection. Of these, ~83 should be randomly allocated to the rapid near patient test (Binax NOW); the remainder will be randomised to the group tested by traditional methods. Thus the speed of diagnosis, impact of early diagnosis on prescribing, clinical outcomes, and costs will be assessed in groups having an estimated 83 and 166 subjects. However, as identical sample sets will be taken from each participant, the diagnostic accuracy of the tests will be assessed in all 249 subjects. The number of cases of *S. pneumonaie* infection that are likely to be identified among the anticipated 649 (556 +93) participants with unspecified acute lower respiratory tract infections is unknown, but their occurrence will add to the pool of cases for studies of diagnostic accuracy.
- On the basis of the Rochester study, we expect that 10% of the 2752 elderly (≥65 years) participants will have influenza A or B. Of the 275, one third (~92) will be allocated to the QuickView near patient influenza immunoassay; one third will be allocated to the rapid molecular group; the remainder will be allocated to the group tested by traditional methods. Identical sample sets will be taken from each individual, so the diagnostic accuracy of the tests will be assessed in all 275 subjects.
- Similarly, we expect that 5% of the 2752 elderly (≥65 years) participants will have RSV A or B. Of the 138, one third (~46) will be allocated to the rapid molecular group; the remainder (~92) will be allocated to the group tested by traditional methods. We expect that very few of these will be found

positive by the routine tests employed. Identical sample sets will be taken from each individual, so the diagnostic accuracy of the tests will be assessed in all 138 subjects.

While the numbers of patients with influenza and RSV who are allocated to the 'rapid' near patient or molecular tests are comparatively small (~92 + ~46 per elderly group, plus cases occurring in the 18-64-year-olds), the impact of a 'viral' infection (RSV or influenza) infection on patient isolation, antimicrobial prescribing, and clinical outcomes may be compared using a larger combined group – i.e.,

Elderly

Rapid influenza & RSV (i.e., Quickview + molecular tests) n=(92+92+46)=230Traditional influenza & RSV n=(92+46+46)=184

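### The optional pooled rapid v traditional viral comparison sets 80% influenza against 50% influenza, so 30% of any influenza–RSV difference would look like a test effect

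*Protocol*

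**What the plan says.** Section 7.1 (Expected number of cases) states for influenza that "we expect that 10% of the 2752 elderly (≥65 years) participants will have influenza A or B" and that "one third (~92) will be allocated to the QuickView near patient influenza immunoassay", with equal shares going to the molecular and culture groups. For RSV it states that "we expect that 5% of the 2752 elderly (≥65 years) participants will have RSV A or B", of whom "one third (~46) will be allocated to the rapid molecular group". The Synopsis (Analysis, Sample size) says where the other RSV cases are counted: "the remainder (~90) will be allocated to the groups tested by traditional methods (Group 1 & 3".

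Both places then offer a pooled comparison as the response to small viral subgroups. The Synopsis says that the impact of viral infection "may be compared using larger combined groups", and section 7.1 says that its impact on isolation, "antimicrobial prescribing, and clinical outcomes may be compared using a larger combined group". The composition is written out:

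- Rapid, elderly: 92 + 92 + 46 = 230 (Synopsis: 91 + 91 + 45 = 227).
- Traditional, elderly: 92 + 46 + 46 = 184 (Synopsis: 91 + 45 + 45, printed as 182).
- Ages 18–64 (section 7.1): 12 + 12 + 6 = 30 rapid and 12 + 6 + 6 = 24 traditional.

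No adjustment for virus is stated for this comparison. The covariates named in section 7.6 are demographics and baseline clinical characteristics, and they are named for comparisons between the three diagnostic groups.

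**The concern.** Group 1 receives a rapid influenza test but no rapid RSV test. The pooling therefore puts its influenza cases on one side and its RSV cases on the other. Membership of a set depends on the randomised group and the virus together, so randomisation no longer balances the two sides for virus. The imbalance is built in and does not shrink with sample size.

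If influenza and RSV patients differ in stay, isolation or prescribing for reasons unrelated to testing, the pooled contrast shows a difference even when testing does nothing. The protocol cannot assume that they do not differ. Their similarity is one of its own hypotheses to be examined (section 2.2): "The clinical characteristics and economic burden of influenza A and B and RSV A and B are similar". One outcome, use of neuraminidase inhibitors, is defined in influenza only (section 7.5.1). A positive pooled result could then not be attributed to rapid testing alone.

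**Working it through.** **Inputs.** 2752 elderly participants, influenza 10%, RSV 5%, three equal groups (section 7.1); length-of-stay SD of 6 days (section 7.4). Co-infection is ignored, as in the protocol's own counts.

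**1. Reproduce the plan's figures.**
- Influenza per group: 0.10 × 2752 / 3 = 91.7, about 92.
- RSV per group: 0.05 × 2752 / 3 = 45.9, about 46.
- Rapid: 2 × 92 + 46 = 230. Traditional: 92 + 2 × 46 = 184. Both agree with section 7.1.
- In the Synopsis, 91 + 45 + 45 is 181, not 182. This is immaterial.

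**2. Influenza share on each side.**

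| Set | Rapid | Traditional | Gap |
|---|---|---|---|
| Elderly, section 7.1 | 184/230 = 80.0% | 92/184 = 50.0% | 30 points |
| Elderly, Synopsis | 182/227 = 80.2% | 91/181 = 50.3% | 30 points |
| Ages 18–64 | 24/30 = 80% | 12/24 = 50% | 30 points |

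As randomised, each group has 92 + 46 = 138 viral cases, of which 92/138 = 66.7% are influenza. The gap comes from the pooling.

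**3. Spurious difference with no test effect.** Let F and R be the mean outcomes in influenza and RSV.

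(0.80 F + 0.20 R) − (0.50 F + 0.50 R) = 0.30 × (F − R)

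**4. Illustration for length of stay.** The protocol gives no value for F − R, so 1, 2 and 3 days are assumptions. The standard error of the pooled contrast is 6 × √(1/230 + 1/184) = 0.59 day. False-positive rates use a normal approximation and a two-sided 5% test.

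| Assumed F − R | Spurious difference | False-positive rate |
|---|---|---|
| 1 day | 0.3 day | about 8% |
| 2 days | 0.6 day | about 17% |
| 3 days | 0.9 day | about 33% |

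**5. Cost of removing the bias.** Effective size is n1 × n2 / (n1 + n2).
- Crude pooling: 230 × 184 / 414 = 102.2.
- Stratified by virus: influenza 184 × 92 / 276 = 61.3, RSV 46 × 92 / 138 = 30.7, sum 92.0.
- Groups 1 and 2 v Group 3 as randomised: 276 × 138 / 414 = 92.0, with 66.7% influenza on both sides (184/276 and 92/138).
- Ratio of standard errors: √(102.2 / 92.0) = 1.05.

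**The case against.** The strongest reply is that this is hardly a planned analysis. It sits in a section on expected numbers and in the matching Synopsis text, it is worded as something that may be done, no power statement in section 7.4 rests on it, and it does not appear in sections 7.5 or 7.6. Those sections compare Groups 1, 2 and 3 for time to a single room and time to no antibiotics in influenza or RSV patients, where the expected virus mix is the same in every group. They also take length of stay and quality of life by group separately for each virus. All of that stands, and it limits the reach of the point.

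A second reply is that no method is given for the pooled comparison, and that a virus term could be left to the statistical analysis plan. This stands only in part. The protocol does not exclude such a term, but it fixes the membership of the two sets, and the confounding lies in that membership.

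A third reply is that influenza and RSV patients may differ little when nobody knows the virus. Section 1.4 describes RSV illness as clinically indistinguishable from influenza, and section 7.1 expects routine tests to find very few RSV cases. This is a fair reason to expect small differences, particularly in isolation and prescribing, but similarity remains a hypothesis of the study.

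The size also needs care. A reader might take a large virus difference in isolation, say 20 points, and infer a false effect of 6 points. That is hard to square with the 5% starting level in section 7.4. If 5% is the no-effect rate at a 2:1 influenza-to-RSV mix, the gap is at most 7.5 points with influenza higher (5 / (2/3)) or 15 with RSV higher (5 / (1/3)). The leakage is then at most 0.30 × 7.5 = 2.25 or 0.30 × 15 = 4.5 points.

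**Conclusion.** The point holds for the optional pooled comparison only. As composed, its sets are 80% and 50% influenza and are not a randomised contrast. If they are compared without regard to virus, 30% of any influenza–RSV difference is carried into the apparent test effect.

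A reader might infer that the whole of a virus difference would pass for a test effect, or that the trial's main viral analyses are biased. The documents support neither: the fraction is 0.30, and the analyses in sections 7.5 and 7.6 keep the randomised groups. Nor do they support a false effect close to the 1-day target difference in stay. That needs an assumed 3-day virus difference, half the stated SD, and the 1-day target belongs to the all-patient comparison. With a 1-day virus difference the false-positive rate is about 8%.

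The 80% and 50% shares follow from the protocol's counts. The size of the bias rests on the assumed virus differences, which the protocol does not give. This is a minor to moderate issue, worth correcting because the pooling is offered as the answer to small viral subgroups across isolation, prescribing and clinical outcomes.

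**What to change.** Amend the Synopsis (Analysis, Sample size) and both the elderly and 18–64 blocks of section 7.1 in one of two ways.

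- **Stratify by virus.** State that rapid and traditional will be compared within influenza (Groups 1 and 2 v Group 3, 184 v 92 in the elderly) and within RSV (Group 2 v Groups 1 and 3, 46 v 92), and that the two estimates will be combined by a stratified log-rank test or Cox model, Mantel–Haenszel, or regression with a virus term. Add Group 2 v Group 3 (46 v 46) as a sensitivity analysis for RSV, because teams caring for Group 1 patients still receive a rapid influenza result.
- **Or pool by randomised group.** Compare Groups 1 and 2 with Group 3 in all viral cases (276 v 138). This balances virus in expectation. It answers a question about testing policy, since Group 1 RSV cases then count as rapid without having had a rapid RSV test.

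Either way the effective size falls from 102 to 92, about a 5% larger standard error. No new patients or data are needed. The stratified version also needs a rule for patients positive for both viruses.

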#### 18-64 year-olds with high-risk conditions

We estimate the total number of admissions in this group to be ~386, with 10% having influenza (n=~38), and 5% having RSV (n=~19) Rapid influenza & RSV (i.e., Quickview + molecular tests) n=(12 + 12 + 6) = 30

Traditional influenza & RSV n=(12+6+6)=24

#### 7.2 Background demographics

Demographic assessments including age, sex, ethnicity and other baseline characteristics (height, weight, smoking habits, alcohol consumption, 'high risk' chronic medical conditions, immunisation status, household size and makeup, contact with children, number of hospital admissions during the previous winter) for the whole study population will be summarised and tabulated. *'High risk'* heart and lung conditions are defined as follows :-

Those with chronic respiratory disease, including asthma	This includes chronic obstructive pulmonary disease (COPD, including chronic bronchitis and emphysema, bronchiectasis, cystic fibrosis, interstitial lung fibrosis, pneumoconiosis,
	asthma requiring continuous or repeated use of inhaled or systemic steroids or with previous exacerbations requiring hospital admission
Those with chronic heart disease	This includes chronic ischaemic heart disease, congenital heart disease and hypertensive heart disease requiring regular medication and follow-up (but excluding uncomplicated controlled hypertension), and chronic heart failure.

#### 7.3 Definitions of influenza, RSV and S. pneumoniae positivity

Influenza positive Patients will be considered influenza positive if:

- The Quidel QuickVue Influenza A and B test is positive, and/or
- The multiplex PCR is positive, and/or
- Viral culture is positive, and/or
- Serology results indicate influenza infection (e.g., 4-fold increase in influenza A H3N2, H1N1, or influenza B HI antibody from acute to convalescent sera).

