### ANALYSIS

The sample size is based on the admissions during 2002-03 and 2003-04 (September 1 – April 30) for elderly ( $\geq$ 65 years old) patients with acute cardio-pulmonary conditions, excluding angina and myocardial infarction. There were 2762 acute cardio-pulmonary admissions during September 1 – April 30 2002-03, and 2852 during 2003-04, i.e., an average of 11.57 admissions ( $\geq$ 65 years) per day.

The study will run for at 666 days (242 during each of Years 1 and 2, and 183 during Year 3), i.e., the number of eligible patients is estimated at 666x11.57=7705.6. We plan to recruit 5 days per week, which reduces the eligible number of patients to  $(5\div7)x7705.6=5504$ . We understand that two-thirds are admitted during the period 09:00-21:00h, which reduces the evaluable pool to 3669. We estimate that three-quarters of eligible subjects will participate, i.e., we expect to recruit 2752 elderly ( $\geq 65$  years old) patients with acute cardio-pulmonary conditions. Of these, 664 are expected to have ICD codes for pneumonia; 556 are expected to have exacerbations of chronic obstructive pulmonary disease; and 735 are expected to be admitted with heart failure.

We estimated the number of admissions in 'high-risk' 18-64 year-olds by extrapolation using (i) national cardio-pulmonary hospital admission data for patients aged 15-59 years, 60-74 years, and 75 years and older and (ii) the number of cardio-pulmonary admissions aged  $\geq$ 65 years in Leicester.

	We assumed that half of the patients admitted with pneumonia, unspecified lower respiratory tract infections, and exacerbations of COPD have underlying high-risk conditions. We expect to recruit 83 18-64-year old patients with pneumonia, 93 with unspecified lower respiratory tract infections, and 181 with COPD. These have not been included in the following estimates: On the basis of historical data we expect that one-third of elderly patients with pneumonia have pneumococcal disease (i.e., 221) but expect the
	number identified by the pneumococcal antigen test to be higher. Of the 221, ~73 should be randomly allocated to the rapid near patient test (Binax NOW) (Group 1); the remainder will be randomised to the group tested by traditional methods (Groups 2 & 3). However, as identical sample sets will be taken from each individual, diagnostic accuracy will be assessed in a minimum of 221 subjects.

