#### **1.6** Diagnostic tests for influenza

Viral isolation and haemagglutination inhibition antibody testing are standard methods for influenza diagnosis, but have drawbacks. Virus isolation by culture from respiratory secretions may take a week or

more (a median of 8 days in one recent study); it requires specialised laboratory facilities; and does not provide results that could influence the initiation of treatment. Serology provides a retrospective diagnosis. Neither test alone is considered a 'gold standard' for influenza diagnosis, since each lacks sensitivity, but culture and serology together have been used as 'gold standard' to assess molecular diagnosis.

Tests for rapid diagnosis of influenza A and B virus by immunofluorescence of exfoliated nasopharyngeal cells have shown variable sensitivity (40 to 100%) and specificity (86 to 99%); they require specialist equipment and expertise and are labour intensive. Rapid, near-patient tests for influenza vary in complexity, sensitivity, and specificity. They can aid clinical management, but their value in the hospital setting in influencing prescribing and infection control is unclear. We plan to use the Quidel QuickVue influenza A and B test. It is the most rapid of the near patient tests; is particularly simple to perform; and has a median sensitivity and specificity of 80%. Its diagnostic accuracy in the elderly is unknown. Molecular diagnosis of influenza by reverse transcription PCR (RT-PCR) provides improved sensitivity and specificity, allows accurate detection, and facilitates the subtyping of influenza. Multiplex PCR has the added advantage of allowing identification of several infectious agents (e.g., influenza subtypes A/H1N1, A/H3N2, and B, and RSV types A and B) in one sample and in one reaction. The technique is used routinely within the specialist diagnostic facilities of the Health Protection Agency, Colindale, where it has a sensitivity of 92% and specificity of 84%. We plan to evaluate the ease of use and usefulness of PCR in Leicester as part of the process of distributing it more widely.

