#### 2. NASOPHARYNGEAL SPECIMENS

One (1) nasal, and one (1) nose and throat swab sample will be collected from all study participants. (See Appendix VIII) The nasal swab can be found in the The Quidel QuickVue Influenza A+B test kit, which is included in the sequentially numbered study packs. Similarly, nose and throat swabs for collection of nasopharyngeal specimens will be found in the participant's study pack. They will be used as follows:

• **GROUP 1 ONLY**: The swab in the Quidel QuickVue Influenza A+B test kit will be used in *one nostril only*, specifically to collect a nasal sample – for rapid near patient testing, in the MAU/ward, of participants in Group 1.

Patients randomised to Group 1 will have near patient tests for influenza A and B antigen done by the study nurse in an area of the MAU/ward where clinical tests such as urinalysis are done routinely. The instructions for collecting the Quidel QuickVue nasal sample and doing all tests are provided in Appendix IX. On completion of the test the Study nurse will:

- (a) Record the test result in the CRF;
- (b) Inform the team (i.e., the responsible nurse and/or doctor) that is providing clinical care of the patient of the rapid near patient test result (i) verbally; and (ii) by insertion of an adhesive label in the notes. The clinical team should be told that a negative test does not exclude infection with influenza A or B.
- (c) Document in the CRF the time that the team was informed, and who was told.
- **GROUPS 1, 2, and 3**: The nose and throat swabs for the molecular tests and traditional tissue culture studies (for influenza and RSV) will be used to swab the throat and *the opposite nostril* (i.e., ONE nostril only) to that used previously and placed in virus transport medium. The instructions for collecting the nose and throat sample are provided in Appendix VIII. The nose and throat sample will be collected from ALL study participants, specifically for:
  - Prompt, conventional viral culture (Groups 1, 2, and 3);
  - Prompt, rapid molecular testing for influenza A and B and RSV A and B (Group 2);
  - Deferred, molecular testing for influenza A and B and RSV A and B (Groups 1 and 3);
  - Deferred Quidel QuickVue test for influenza A and B (Groups 1 and 2)
  - Possible future tests for other respiratory pathogens of stored specimens, if tests for influenza, RSV, and *S. pneumoniae* are negative.

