#### **RSV positive** Patients will be considered RSV positive if:

The multiplex PCR is positive, and/or

- Viral culture is positive, and/or
- Serology results indicate RSV infection (e.g., ≥4-fold increase in RSV antibodies from Day 1 to Day 30).

S. pneumoniae positive Patients will be considered influenza positive if:

- The Binax NOW S. pneumoniae antigen test is positive, and/or
- Blood culture is positive, and/or
- Sputum culture is positive, AND the sputum sample is macroscopically purulent, AND the sputum sample reveals increased numbers of polymorphonuclear leucocytes, AND the Gram stain is positive, AND there is moderate-to-high amounts of growth, according to criteria used by the laboratory.

Evaluations will be based on: (i) populations whose cardio-pulmonary illness is confirmed as due to influenza, RSV or *S. pneumoniae*, and (ii) the study groups comprising all people who are investigated by the different strategies under investigation (rapid near patient tests, *versus* rapid molecular diagnosis, *versus* conventional laboratory tests).

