#### 7.6 Statistical analysis

All analyses for both process and clinical outcomes will be based on Intention to Treat (ITT) analyses.

Impact of test result on prescribing The time to prescription of `narrow spectrum', `oral antibiotics' or `no antibiotics' between the three groups will be assessed using survival analysis techniques, whilst the use of neuraminidase inhibitors in those with influenza will be assessed using  $\chi^2$  tests, together with 95% CIs. Further analyses to allow for potential differences in patient demographics and baseline clinical characteristics between the three diagnostic test groups, and not allowed by stratification, will make use of cox proportional hazards regression modelling in the case of time to appropriate prescribing and logistic regression techniques in the case of neuraminidase inhibitors.

*Length of hospital stay* Length of hospital stay in the three diagnostic groups will initially be compared using non-parametric methods. Further analyses to allow for potential differences in patient demographics and baseline clinical characteristics between the three diagnostic test groups, and not allowed by stratification, will make use of generalised linear models in order to accommodate any skewness in the data.

*Mortality rates* Mortality rates between the three diagnostic testing groups will be compared by means of a Log-Rank Test and Kaplan-Meier survival curves. Adjustment for potential differences in patient demographics and baseline clinical characteristics between the three diagnostic test groups, and not allowed by stratification, will make use of Cox proportional hazards regression methods.

*Diagnostic accuracy* Sensitivity, specificity, positive predictive value of molecular and near patient diagnostic tests in comparison to traditional laboratory methods will be calculated together with 95% CIs. Heterogeneity in the sensitivity and specificity with respect to patient demographics and baseline clinical characteristics will be explored as secondary analyses using patient defined sub-groups.

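### Section 7.3 lets the Group 1 bedside tests decide on their own who counts as infected, although those tests are not run alike in all arms, so infection-restricted comparisons can have arm-dependent denominators

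*Protocol*

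**What the plan says.** **Case definitions.** Section 7.3 joins its criteria by and/or, so one positive result suffices and no confirmation is needed. For influenza: "The Quidel QuickVue Influenza A and B test is positive, and/or", then multiplex PCR, culture or a serological rise. For *S. pneumoniae*: "The Binax NOW S. pneumoniae antigen test is positive, and/or", then blood culture or a set of sputum criteria. RSV rests on PCR, culture or serology, with no near-patient test.

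**Endpoints that use them (7.5.1, 7.5.2, 7.6).** Time to no antibiotics; neuraminidase inhibitor use; time to a single room and isolation within 120 hours; intensive care, ventilation and death in *S. pneumoniae* patients; and the infection-subgroup versions of stay, quality of life and cost.

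**How the tests are run.** Section 4.1 says that every test will eventually be done on every patient. Section 6.1.14 differs:
- Nasopharyngeal specimens: "Deferred Quidel QuickVue test for influenza A and B (Groups 1 and 2" is the entry for the deferred test, so Group 3 is not named. The deferred test uses swabs placed in virus transport medium. The kit instructions in Appendix IX forbid transport media and limit storage to eight hours.
- Urine: Binax is done on the ward in Group 1, with no mention of concentration. It is done on concentrated urine in the laboratory in Groups 2 (fresh) and 3 (stored). The laboratory urine instructions name Groups 2 and 3 only.

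**Accuracy analysis.** Section 7.6 compares with traditional laboratory methods ("positive predictive value of molecular and near patient diagnostic tests in comparison to traditional laboratory methods will be calculated together with 95% CIs"). Section 7.5.3 compares with traditional and other tests, giving serology as an example.

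**The concern.** In Group 1 the QuickVue or Binax result is the randomised intervention, it drives the clinical team's response, and it can by itself put the patient in the subgroup in which that response is measured. Two problems follow.

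1. **Arm-dependent denominators.** If the same bedside test is not applied in Groups 2 and 3, or is applied to a different specimen, then the patients labelled infected are not comparable across arms, and randomisation no longer protects comparisons within that label.
2. **Action on a false result is scored as benefit.** An uninfected Group 1 patient with a false-positive QuickVue enters the influenza denominator and, if isolated or given an antiviral, the numerator too. This persists even if every test is eventually run in every arm.

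What is at stake is whether the infection-restricted prescribing and isolation endpoints can tell an accurate test from a poor one. Isolation is also one of only two clinical endpoints with a power statement in section 7.4.

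**Working it through.** **Plan's own figures.** 666 days × 11.57 × 5/7 × 2/3 × 3/4 = 2752, matching "we expect to recruit 2752 elderly". For influenza, "We expect that 10% of the 2752 (elderly) patients will have influenza A or B": 2752 × 0.10 = 275, or 92 per arm (the protocol gives about 91 or 92). These counts are sample size times prevalence, so they allow for no false positives, which an any-positive rule will produce.

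**Inputs.** Per arm 2752/3 = 917, of whom 91.7 are infected and 825.6 are not. Section 1.6 says of QuickVue that it "has a median sensitivity and specificity of 80" per cent, and of PCR that "it has a sensitivity of 92% and specificity of 84" per cent. Appendix X gives Binax specificity of 94% (retrospective study) and 71% (hospitalised patients, prospective study). Assumptions: tests err independently given true status; culture and serology add no cases, true or false.

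**Influenza.** True positives = 91.7 × [1 − product of (1 − sensitivity)]; false positives = 825.6 × [1 − product of specificities].
- QuickVue and PCR: 91.7 × (1 − 0.20 × 0.08) = 90 true; 825.6 × (1 − 0.80 × 0.84) = 271 false; total 361, 25% true.
- PCR without QuickVue: 91.7 × 0.92 = 84 true; 825.6 × 0.16 = 132 false; total 216, 39% true.

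Range, holding sensitivities fixed (rows after the first use assumed values for at least one specificity):

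| Specificity QuickVue / PCR | Arm with QuickVue | Arm without |
|---|---|---|
| 80% / 84% | 361 (25% true) | 216 (39%) |
| 90% / 84% | 292 (31%) | 216 (39%) |
| 90% / 100% | 173 (52%) | 84 (100%) |
| 98% / 99% | 115 (79%) | 93 (91%) |

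**Scoring of isolation.** As an illustration, assume that QuickVue positives known to the ward are isolated at 15% and everyone else at 5%. These rates echo section 7.4, where they are policy-level targets. At 80%/84% specificity, Group 1 has 0.80 × 91.7 + 0.20 × 825.6 = 73.4 + 165.1 = 238.5 QuickVue positives. The labelled isolation rate is (238.5 × 0.15 + 122.6 × 0.05)/361.1 = 11.6%. Group 3 stays at 5% whether or not its swabs are tested later, because the ward does not know the result. Of the isolations that follow a positive QuickVue, 165.1/238.5 = 69% are of uninfected patients (18% at 98% specificity).

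Among the truly infected, the Group 1 rate would be 0.80 × 15% + 0.20 × 5% = 13%. Now take a worthless test, positive in 20% of patients whatever their status. It gives 183.5 positives and 91.7 × (1 − 0.80 × 0.08) + 271 = 357 labelled cases. The labelled rate is (183.5 × 0.15 + 173.2 × 0.05)/356.7 = 10.1%, against 7% among the truly infected. The label thus narrows the gap between a useful and a worthless test from 13% v 7% to 11.6% v 10.1%.

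**Pneumococcus.** With 221 true cases (synopsis), all assumed found:
- All 2752 tested: 2531 × 0.06 = 152 false (41% of positives); 2531 × 0.29 = 734 false (77%).
- The 664 pneumonia patients only: 443 × 0.06 = 27 (11%); 443 × 0.29 = 128 (37%).

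**The case against.** **The arm difference in influenza may be a slip.** A deferred repeat for Group 1, which has already had the bedside test, makes little sense, and section 4.1 says all tests are done on all patients. Groups 2 and 3 may have been meant. This stands to the extent that 361 v 216 should not be read as what the trial will deliver. It does not remove the difference in specimen: the deferred test would still use transport-medium swabs, and Binax would still differ in setting and urine preparation. Nor does it remove the scoring problem.

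**The specificities are soft.** Section 1.6 says that QuickVue accuracy in the elderly is unknown and that culture and serology each lack sensitivity, so some apparent PCR false positives may be real infections. Binax was judged against blood culture, which section 1.8 says is positive in under 10% of community-acquired pneumonia. A reader might infer that the subgroups are mostly false positives; the documents do not establish that.

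**Any-positive composites are defensible where no gold standard exists.** True for describing burden. It does not justify letting a result that is both the intervention and the trigger for action define the denominator of a between-arm comparison.

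**The accuracy analysis.** A reader might infer from section 7.6 that culture is the sole reference, so that Hypothesis 1 could never be shown. Section 7.5.3 already admits serology, so that does not follow; the two sections need aligning. Nothing in the documents requires discrepant analysis to be removed.

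**Scope.** Time to narrow-spectrum and to oral antibiotics concerns patients prescribed antibiotics, and stay, quality of life and care costs are also assessed in all patients. Both points stand.

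**Conclusion.** The concern holds for influenza and *S. pneumoniae* in comparisons between groups restricted to infected patients. Following section 7.3 as written allows denominators that depend on the arm and credits action taken on a false bedside result. Whole-group intention-to-treat analyses are untouched. RSV membership does not differ by arm in the tests used, since the same PCR is planned for everyone and only its timing differs.

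The mechanism is certain; the size is not. For influenza the label ranges from 361 (25% true) v 216 (39%) at the protocol's own specificities to 115 (79%) v 93 (91%) at assumed values of 98% and 99%. Both contrasts assume independent errors and an arm without QuickVue. The pneumococcal false share runs from about 11% to 77%, depending on which kit specificity applies and who is tested. The isolation illustration rests on assumed 15% and 5% rates. It shows mainly a loss of discrimination between good and poor tests, and not always an inflated effect.

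**What to change.** **Influenza, between-group endpoints.** Define a case by PCR, culture or a paired serological rise, on the same specimen type in every arm, excluding the near-patient QuickVue result. Because PCR is Group 2's own randomised test, add a sensitivity analysis on culture and/or paired serology only. Isolation is assessed in influenza and RSV together, so that analysis should cover RSV as well.

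***S. pneumoniae*, between-group endpoints.** Exclude the bedside Binax result. Use blood culture or the sputum criteria already in section 7.3. Add antigen only if the same laboratory assay on the same urine preparation is applied in all three groups, which means sending Group 1 urine to the laboratory too.

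**Reconcile the text.** Bring the deferred QuickVue and urine entries in 6.1.14 into line with 4.1, and 7.6 into line with 7.5.3, so that the accuracy reference is culture and/or paired serology and never includes the index test.

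**Cost.** Mostly rewording: PCR, culture, serology, and blood and sputum culture are already planned in every group. There will be fewer labelled cases. The loss could be severe for pneumococcus, since section 1.8 says that few patients produce sputum, that its yield is below 25%, and that blood cultures are seldom positive. Convalescent serum comes only from survivors, so serological classification will be incomplete. PCR remains prompt in Group 2 and deferred in Groups 1 and 3, a storage difference that the change does not remove.
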